**Programmer Note:**

***For Tables 14.2.5.1.4 through 14.2.5.1.6, aPTT baseline will be the average of all pre-dialysis aPTT value on Days -7, -5, -3 and 1, and the change from baseline will be calculated as follows: (post-dialysis/baseline).***

Table 14.2.5.1.7	Individual and Mean Difference Between Pre- and Post-dialysis aPTT Values (unit) – Days -7 to 12 – 0.25 mg/kg Xisomab 3G3 on Day 1 (Safety Population)
Table 14.2.5.1.8	Individual and Mean Difference Between Pre- and Post-dialysis aPTT Values (unit) – Days -7 to 12 – 0.5 mg/kg Xisomab 3G3 on Day 1 (Safety Population)
Table 14.2.5.1.9	Individual and Mean Difference Between Pre- and Post-dialysis aPTT Values (unit) – Days -7 to 12 – Placebo (Pooled) (Safety Population)

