| | Hours → | | start | end | start | end | start |
| Safety Evaluations | | | | | | | |
| Abbreviated Physical Examination ^{e:} | | | | | | | X ^{r:} |
| Weight | | X ^{f:} | X ^{g:} | X ^{f:} | X ^{g:} | X ^{f:} | X ^{g:} |
| 12-Lead Safety ECG | | | | | | | X ^{r:} |
| Vital Signs (HR, BP, RR, and T) | | X ^{f:} | | X ^{f:} | | X ^{f:} | X ^{r:} |
| Bleeding of Access Site | | | | | | | X ^{g:} |
| Hem, Serum Chem ^{h:} , and UA ^{i:} | | | | | | | X ^{r:} |
| Coagulation ^{j:} | | | | | | X ^{f:} | X ^{g:} |
| Platelet Count ^{s:} | | | | | | X ^{f:} | X ^{g:} |
| Serum Pregnancy Test (♀ only) | | | | | | | X ^{r:} |
| AE Monitoring | | | | X | | | X |
| ConMeds Monitoring | | | | X | | | |
| Study Drug Administration / PK/PD/Immunogenicity | | | | | | | |
| Blood for free xisomab 3G3 PK | | | | | | | X ^{r:} |
| Blood for free xisomab 3G3 PD (aPTT) ^{s:} | | X ^{o:} | | X ^{o:} | | | |
| Blood for Immunogenicity | | | | | | | X ^{r:} |
| Other Procedures | | | | | | | |
| Blood BUN and Potassium (for Kt/V and URR) | | | | | | X ^{f:} | X ^{g:} |
| Dialysate Analysis | | | | | | X ^{k:} | X ^{k:} |
| Visual Assessment and Processing of Dialyzer Membrane | | | | | | | X ^{l:} |
| Return Visits | | | X | | X | | X |

- a: For details on Procedures, refer to [Section 13](#)
- b: Within 28 days prior to Day -8.
- c: Patients will be admitted to the CRU on Day -8, at the time indicated by the CRU and will remain confined up to Day 6 or prior early termination.
- d: Patients will undergo hemodialysis 3 times a week, on Day -7, Day -5, Day -3, and Day 1, Day 3, Day 5, Day 8, Day 10, and Day 12. For each patient, the hemodialysis will last at least 3 hours as per patient standard schedule which will be the same throughout the study.
- e: Symptom-driven physical examination may be performed at other times, at the PI's or designee's discretion.
- f: To be performed ~ 1 hour prior to the start of hemodialysis.
- g: To be performed at the end of hemodialysis.
- h: Samples for serum chemistry will be obtained following a fast of at least 4 hours, however, in case of dropouts or rechecks, patients may not have fasted for 4 hours prior to the serum chemistry sample is taken.
- i: For anuric patients, urinalysis may not be performed.
- j: Coagulation parameters (activated partial thromboplastin time [aPTT], prothrombin time [PT], and international normalized ratio [INR]).

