- k: The dialysate sample will be taken at 30 minutes and at 3 hours after the start of hemodialysis. The dialysate will be freeze and sent to Aronora.
- l: To be performed when the dialyzer cartridge is removed and collected at the end of HD.
- m: To be performed prior to dosing.
- n: A single dose of xisomab 3G3 or matching placebo will be administered at Hour 0. The dose will be injected through a port into the flowing arterial blood in the proximal dialysis line according to the randomization schedule, immediately after the start of HD.
- o: When the PK or PD sample is on an HD day, the sample should be taken at least 1 hour prior the start of HD session. The actual time will be recorded.
- p: To be performed at discharge or early termination; the PK and aPTT should be taken at 120 hour postdose.
- q: The vascular access sites (AV fistula or AV graft puncture sites) are to be evaluated immediately after the end of HD and removal of the needles from the fistula or graft for bleeding cessation or other reactions.
- r: All patients who received the study drug or placebo (including patients who terminate the study early) will undergo follow-up procedures at the Clinical Research Unit (CRU) approximately 12 days after dosing, as they return for their last HD. Events performed on Day 12 can be performed at end of HD if more appropriate.
- s: Platelet count, BUN and potassium, and aPTT value will be taken from the hematology, serum chemistry, and coagulation sample, respectively, when these are scheduled to be collected at the same time. Samples will not be taken twice at a same timepoint.

Abbreviations: ♀ = Females, AE = Adverse events, BUN = Blood urea nitrogen, BP = Blood pressure, C-I = Check-in, Chem = Chemistry, ConMeds = Concomitant medication, CRU = Clinical research unit, ECG = Electrocardiogram, FSH = Follicle-stimulating hormone, FU = Follow-up, Hem = Hematology, HD = Hemodialysis, HIV = Human immunodeficiency virus, HR = Heart rate, Kt/V = ratio of volume of fluid completely cleared of urea, PD = Pharmacodynamic, PK = Pharmacokinetics, PMP = Postmenopausal, RR = Respiratory rate, T = Temperature, UA = Urinalysis, URR = Urea reduction ratio.

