8.4.2 Rationale for the Dose Selection

Doses of 0.25 mg/kg and 0.5 mg/kg were selected for this phase 2 study in order to provide adequate PD and PK characterization but still allowing a safety margin should the results differ in this population compared to healthy subjects. The 0.25 mg/kg xisomab 3G3 dose is 2.5-fold higher than the lowest dose in the FIH study. The 0.1 mg/kg dose in the FIH study had a short and modest, yet detectable PD effect (several seconds of temporal aPTT prolongation). The 0.25 mg/kg dose is expected to provide an initial plasma concentration that is within the range of average FXI concentration, the molecular target of xisomab 3G3, in human subjects, and may approach saturation in some individuals after full distribution. Therefore, it has the potential to exert brief pharmacological (anti-inflammatory, antithrombotic) activity, possibly lasting up to a day, until elimination of the antibody and hepatic FXI secretion that neutralizes the antibody.

The 0.5 mg/kg dose was safely administered in the FIH study and allowed adequate characterization of the PK profile in healthy adults. In addition, following a 0.5 mg/kg a prolongation of aPTT was seen, with highest values measured at 24 hours postdose and having a sustained effect for at least 72 hours postdose. The 0.5 mg/kg xisomab 3G3 dose is expected to provide, after complete distribution, a plasma concentration that is approximately twice the average human plasma concentration of the FXI antigen. Therefore, this dose is expected to be overcome by FXI generation later, and have pharmacological activity that lasts longer than the lower dose level.

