14.3.3 Pharmacodynamic Analyses

Placebo patients from Cohort 1 and Cohort 2 will be pooled for analysis.

The PD analysis will include assessments of drug potency and efficiency of HD. These will include change in aPTT, BUN, and potassium levels. Change in thrombus accumulation, in total dialysate urea, URR, and Kt/V after xisomab 3G3 levels versus pre-treatment and placebo will also be evaluated. Total protein accumulation within HD filter will be evaluated.

The change from baseline in PD endpoints will be summarized by treatment (2 active dose levels and pooled placebo) and at each scheduled time point using descriptive statistics. The baseline values are any value observed from Day -7 to Day 1, prior to xisomab 3G3 administration. Any values after a single dose of xisomab 3G3 are regarded as post baseline values.

The change from baseline variables will be calculated as the post-baseline value minus the value at baseline.

Additional analyses may be performed as deemed necessary upon review of the data.

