## 7.2 Data Summarization and Presentation of PD Parameters

### 7.2.1 aPTT

**Sample Collection:** Samples for the coagulation parameter (aPTT) will be collected at screening, pre- and post-dialysis on Days -7, -5, -3, 1, 3, 5, and 12. Additional samples for aPTT will be collected following xisomab 3G3/placebo dosing on Day 1 at predose (hour 0, at least 1 hour prior the start of HD session) and at 0.167, 0.5, 1, 2, 3, 4, 6, 8, 12, 16, 24, 48, 96, 120, 144, and 192, hours after xisomab 3G3 start of infusion.

**Baseline Calculation Method Following Day 1 Dosing:** Following xisomab 3G3 dosing on Day 1, aPTT change from baseline will be calculated by dividing postdose aPTT values from average of pre-dose baseline (the average of pre-dialysis aPTT values on Days -7, -5, -3, and 1 will be calculated as pre-dose baseline).

**Fold change in aPTT values:** The fold change in aPTT values on Days -7, -5, -3, 1 (only pre- and post-dialysis aPTT values on Day 1), 3, 5, and 12 will be calculated by dividing the post-dialysis aPTT/pre-dialysis aPTT values for each day separately.

aPTT values will be extracted from the clinical laboratory database and descriptive statistics will be generated using SAS® version 9.3 or higher. Following Day 1 xisomab 3G3 dosing, a table will be presented for the aPTT change from baseline with descriptive statistics.

aPTT values will be listed and summarized by treatment and time points in Tables and Figures for all subjects in the Safety Population (2 active dose levels and pooled placebo). aPTT values will be presented with the same level of precision as received from the clinical laboratory database. Summary statistics, including n, Mean, SD, CV%, SEM, minimum, median, and maximum will be calculated for all nominal values time points. Excluded subjects will be included in the aPPT values tables, but will be excluded from the summary statistics and noted as such in the tables.

Mean and individual aPTT values-time and change from baseline-time profiles will be presented on linear scale. Linear mean plots will be presented with and without SD.

The level of precision for the aPPT values summary statistic will be presented as follows:

- minimum/maximum: in same precision as in the clinical laboratory database
- Mean/median: in one more level of precision than minimum/maximum
- SD/SEM: in one more level of precision than Mean/median
- n will be presented as an integer
- CV% will be presented to the nearest tenth

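### The programmer note for the aPTT change-from-baseline tables puts the post-dialysis value where SAP 7.2.1 puts each postdose value; read literally, at least 15 of the 16 timed postdose samples drop out of those tables

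*SAP*

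**What the plan says.** SAP 7.2.1 describes two series of aPTT samples. One is a set of pairs taken "pre- and post-dialysis on Days -7, -5, -3, 1, 3, 5, and 12". The other is a timed series around dosing: a predose sample, then "0.167, 0.5, 1, 2, 3, 4, 6, 8, 12, 16, 24, 48, 96, 120, 144, and 192, hours after xisomab 3G3 start of infusion".

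For the effect after dosing, the same section states that "aPTT change from baseline will be calculated by dividing postdose aPTT values from average of pre-dose baseline", where the baseline is the mean of the pre-dialysis values on Days -7, -5, -3 and 1. It treats the post-dialysis to pre-dialysis ratio within a day as a different measure, a fold change.

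Protocol 14.3.3 is equally broad about which values count: "Any values after a single dose of xisomab 3G3 are regarded as post baseline values". It asks for change from baseline at each scheduled time point.

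The programmer note in SAP 10.2 for Tables 14.2.5.1.4 to 14.2.5.1.6 keeps the 7.2.1 baseline but changes the numerator: "the change from baseline will be calculated as follows: (post-dialysis/baseline". The next note, for Tables 14.2.5.1.7 to 14.2.5.1.9, uses the post-dialysis value again, this time correctly, for the within-day fold change.

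**The concern.** The method text and the table-level formula cannot both be followed, and the SAP gives no rule on which prevails. A programmer works from the note attached to the table. In this SAP the note's term names the sample at the end of a dialysis session, not any sample after the dose.

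At stake is the baseline-adjusted summary of one of the secondary potency markers. Protocol 8.4.2 says that 0.5 mg/kg prolonged aPTT in the first-in-human study, with "highest values measured at 24 hours postdose and having a sustained effect for at least 72 hours postdose". For 0.25 mg/kg it expects activity lasting perhaps a day. A table limited to end-of-session values would show neither course relative to baseline.

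**Working it through.** No power or sample-size figure bears on this point. The check is a count of samples.

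**Inputs**
- Timed postdose hours: SAP 7.2.1, quoted above.
- Dialysis days: Protocol Section 6, footnote d, "Day -7, Day -5, Day -3, and Day 1, Day 3, Day 5, Day 8, Day 10, and Day 12".
- Timed samples that fall on a dialysis day: Protocol Section 6, footnote o, "the sample should be taken at least 1 hour prior the start of HD session".
- End of dialysis on Day 1: hour 3 in the protocol flow chart, about 4 hours in SAP Section 9.

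**Reproducing the plan's own count.** The list has 11 times from 0.167 to 24 h and 5 from 48 to 192 h, so 11 + 5 = 16 postdose times. With predose, 16 + 1 = 17. Protocol Table 4 allows up to 17 aPTT-only samples at 2.7 mL, and 17 × 2.7 = 45.9 mL, which matches.

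**Mapping each time to the dialysis schedule**, with study day = whole part of (hour / 24) + 1:

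| Timed sample (h) | Number | Study day | Position relative to dialysis | Can be the post-dialysis draw? |
|---|---|---|---|---|
| 0.167, 0.5, 1, 2 | 4 | 1 | during the session | no |
| 3, 4 | 2 | 1 | one may coincide with the end of the session | at most one |
| 6, 8, 12, 16 | 4 | 1 | hours after the end-of-session draw | no |
| 24 | 1 | 2 | no dialysis that day | no |
| 48 | 1 | 3 | at least 1 h before the session | no |
| 96 | 1 | 5 | at least 1 h before the session | no |
| 120, 144, 192 | 3 | 6, 7, 9 | no dialysis on those days | no |

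Total: 4 + 2 + 4 + 1 + 1 + 1 + 3 = 16. At most 1 is kept, so at least 16 − 1 = 15 are lost. The result is the same whether Day 1 dialysis ends at 3 h or at 4 h.

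**What the literal note would tabulate.** Post-dialysis aPTT after dosing exists on Days 1, 3, 5 and 12, so 4 values per patient. If sessions last 3 to 4 hours and start at hours 0, 48, 96 and 264 (= 11 × 24), these fall at about 3–4, 51–52, 99–100 and 267–268 h. In the first 24 hours, one value replaces 11.

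**A looser reading.** If post-dialysis meant any time from the end of the Day 1 session onward, 12 samples would remain with an end at 3 h (4 lost: 0.167, 0.5, 1 and 2 h), or 11 with an end at 4 h (5 lost: the same plus 3 h). The SAP does not use the term that way, and the early samples would still be missing.

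**The case against.** The strongest reply is that this is a slip of wording and that the intent is plain elsewhere. SAP 7.2.1 gives the right numerator. The table titles refer to the period after the infusion. The tables share the concentration-table shell, with a predose column and sampling times in hours, which post-dialysis values could not fill. The change-from-baseline figures run on hours since the infusion began. All of this stands. It makes the correction unambiguous, but it does not remove the conflict.

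Several stronger readings are tempting, and the documents do not support them:

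- **That the time, size and duration of the aPTT effect could no longer be seen.** Tables 14.2.5.1.1 to 14.2.5.1.3 list individual aPTT values across the study, with means for both active doses (the shell notes omit summary statistics for pooled placebo). Figures 11-4, 11-5 and 14.2.5.2.1 to 14.2.5.2.4 plot mean aPTT over time, and Appendix 16.2.6.2.1 plots each patient.
- **That the change-from-baseline figures carry the same error.** The note names only the tables, and the figure notes do not repeat its formula. Figures 11-6, 14.2.5.2.5 and 14.2.5.2.6 are affected only if they are built from the same derived variable. For the same reason, the tables cannot be called the only planned display against baseline.
- **That aPTT is the main potency endpoint.** It is listed unranked beside thrombus and protein accumulation among the secondary outcomes.
- **That aPTT peaked at 24 hours in the earlier study as a whole.** Protocol 8.4.2 says this for 0.5 mg/kg only.
- **That correcting the note separates the drug effect from the dialysis effect.** Day 1 values drawn during and at the end of dialysis will still be divided by a pre-dialysis baseline. Comparison with placebo has to deal with that.

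**Conclusion.** The note is wrong as written. It states a derivation for a secondary pharmacodynamic measure that contradicts SAP 7.2.1 and does not fit its own table shell. Followed literally, it removes at least 15 of the 16 timed postdose samples from Tables 14.2.5.1.4 to 14.2.5.1.6, including 24 h, and leaves 4 end-of-session values per patient.

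This rests on taking post-dialysis to mean the end-of-session draw, as SAP 7.2.1 and the neighbouring note do, and on Day 1 dialysis ending at about 3 or 4 hours. No data are lost, and the raw time course remains in other tables and figures. The damage is limited to the baseline-adjusted tables, and possibly the three figures named above. It should be corrected before the tables are programmed.

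**What to change.** In the programmer note for Tables 14.2.5.1.4 to 14.2.5.1.6, change the formula to *each postdose aPTT value / baseline*, for every scheduled postdose time point in SAP 7.2.1, with the baseline left as it is. Add that Figures 11-6, 14.2.5.2.5 and 14.2.5.2.6 use the same derivation. Leave the within-day post-dialysis to pre-dialysis ratio in Tables 14.2.5.1.7 to 14.2.5.1.9.

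The cost is a one-line correction and one added sentence in the SAP, with no new data and no protocol amendment.

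The corrected formula is a ratio, in line with SAP 7.2.1. Protocol 14.3.3 defines change as a subtraction, and the figure notes label the axis in seconds. That difference is a separate point to reconcile.

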**Programmer Note:**

***For Tables 14.2.5.1.7 through 14.2.5.1.9, the fold change will be calculated by follows: (post-dialysis/pre-dialysis aPTT values) for each day.***

Figure 14.2.5.2.1	Arithmetic Mean aPPT Values Versus Time Following a Single IV Infusion of 0.25 and 0.5 mg/kg Xisomab 3G3 and Placebo (Pooled) – Day 1 (Linear Scale) (Safety Population)
-------------------	--

- Figure 14.2.5.2.2 Arithmetic Mean (SD) aPPT Values Versus Time Following a Single IV Infusion of 0.25 and 0.5 mg/kg Xisomab 3G3 and Placebo (Pooled) – Day 1 (Linear Scale) (Safety Population)
- Figure 14.2.5.2.3 Arithmetic Mean aPPT Values Versus Time During the Course of the Study – Days -7 to 12 (Linear Scale) (Safety Population)
- Figure 14.2.5.2.4 Arithmetic Mean (SD) aPPT Values Versus Time During the Course of the Study – Days -7 to 12 (Linear Scale) (Safety Population)
- Figure 14.2.5.2.5 Arithmetic Mean aPPT Change From Baseline Versus Time Following a Single IV Infusion of 0.25 and 0.5 mg/kg Xisomab 3G3 and Placebo (Pooled) – Day 1 (Linear Scale) (Safety Population)
- Figure 14.2.5.2.6 Arithmetic Mean (SD) aPPT Change From Baseline Versus Time Following a Single IV Infusion of 0.25 and 0.5 mg/kg Xisomab 3G3 and Placebo (Pooled) – Day 1 (Linear Scale) (Safety Population)
- Figure 14.2.5.2.7 Arithmetic Mean Pre- and Post-dialysis aPTT Values – Days -7 to 12 (Linear Scale) (Safety Population)
- Figure 14.2.5.2.8 Arithmetic Mean (SD) Pre- and Post-dialysis aPTT Values – Days -7 to 12 (Linear Scale) (Safety Population)

#### **14.2.6 Clotting in the Drip Chamber Tables**

- Table 14.2.6.1 Summary of Clotting in the Drip Chamber (Safety Population)

#### **14.2.7 Clotting in Dialysis Filter Tables**

- Table 14.2.7.1 Summary of Clotting in the Dialysis Filter (Safety Population)

### **14.3 Safety Data Summary Tables**

#### **14.3.1 Displays of Adverse Events**

- Table 14.3.1.1 Treatment-emergent Adverse Event Frequency by Treatment – Number of Subjects Reporting the Event (% of Subject Dosed) (Safety Population)

Table 14.3.1.2 Treatment-emergent Adverse Event Frequency by Treatment – Number of Adverse Events (% of Total Adverse Events) (Safety Population)

Table 14.3.1.3 Treatment-emergent Adverse Event Frequency by Treatment, Severity, and Relationship to Drug – Number of Adverse Events (Safety Population)

#### **14.3.2 Listings of Deaths, other Serious and Significant Adverse Events**

Table 14.3.2.1 Serious Adverse Events (Safety Population)

<if no serious adverse event occurred, a statement ‘No serious adverse event is reported’>

#### **14.3.3 Narratives of Deaths, other Serious and Certain other Significant Adverse Events**

#### **14.3.4 Abnormal Laboratory Value Listing (each patient)**

Table 14.3.4.1 Out-of-Range Values and Recheck Results – Serum Chemistry (Safety Population)

Table 14.3.4.2 Out-of-Range Values and Recheck Results – Hematology/Coagulation (Safety Population)

Table 14.3.4.3 Out-of-Range Values and Recheck Results – Urinalysis (Safety Population)

#### **14.3.5 Displays of Other Laboratory, Vital Signs, Electrocardiogram, Physical Examination, and Other Safety Data**

Table 14.3.5.1 Clinical Laboratory Summary and Change from Baseline – Serum Chemistry (Safety Population)

Table 14.3.5.2 Clinical Laboratory Shift from Baseline – Serum Chemistry (Safety Population)

Table 14.3.5.3 Clinical Laboratory Summary and Change from Baseline – Hematology (Safety Population)

Table 14.3.5.4 Clinical Laboratory Shift from Baseline – Hematology (Safety Population)

Table 14.3.5.5 Clinical Laboratory Summary and Change from Baseline – Coagulation and Platelet Count (Safety Population)

Table 14.3.5.6 Clinical Laboratory Shift from Baseline – Coagulation and Platelet Count (Safety Population)

Table 14.3.5.7 Vital Sign Summary and Change from Baseline (Safety Population)

Table 14.3.5.8 12-Lead Electrocardiogram Summary and Change from Baseline (Safety Population)

Table 14.3.5.9 Frequency of Immunogenicity - ADA Titer (Safety Population)

### **10.3 Section 16 Data Listings**

Data listings are numbered following the ICH structure but may be renumbered as appropriate during the compilation of the TFLs for the CSR. The following is a list of appendix numbers and titles that will be included as data listings:

#### **16.1 Study Information**

Appendix 16.1.9 Statistical Methods

Appendix 16.1.10.1 Clinical Laboratory Reference Ranges

#### **16.2 Subject Data Listings**

##### **16.2.1 Subject Discontinuation**

Appendix 16.2.1 Study Completion/Early Termination (Safety Population)

##### **16.2.2 Protocol Deviations**

Appendix 16.2.2 Protocol Deviations

##### **16.2.3 Subjects Excluded from Pharmacokinetic/Pharmacodynamic Analyses**

Appendix 16.2.3 Subjects Excluded from Pharmacokinetic/Pharmacodynamic Analyses

<Note: Appendices 16.2.2 and 16.2.3 are generated in MS Word for inclusion in the study report.>

##### **16.2.4 Demographic Data**

Appendix 16.2.4.1 Demographics (Safety Population)

Appendix 16.2.4.2 Physical Examination (Safety Population)

Appendix 16.2.4.3 Medical and Surgical History (Safety Population)

Appendix 16.2.4.4 Alcohol Screen (Safety Population)

Appendix 16.2.4.5 Drug Screen (Safety Population)

##### **16.2.5 Compliance and/or Drug Concentration Data**

- Appendix 16.2.5.1 Subject Eligibility (Safety Population)
- Appendix 16.2.5.2 Subject Eligibility at Check-In (Safety Population)
- Appendix 16.2.5.3 Test Compound Administration (Safety Population)
- Appendix 16.2.5.4 Blood Draw Times for Free xisomab 3G3 PK (Safety Population)
- Appendix 16.2.5.5 Blood Draw Times for Free xisomab 3G3 PD (aPTT) (Safety Population)
- Appendix 16.2.5.6 Blood Draw Times for Immunogenicity (Safety Population)
- Appendix 16.2.5.7 Blood Draw Times for Dialysate Analysis for Kt/V and URR (Safety Population)
- Appendix 16.2.5.8.1 Dialyzer Assessment (I of V) (Safety Population)
- Appendix 16.2.5.8.2 Dialyzer Assessment (II of V) (Safety Population)
- Appendix 16.2.5.8.3 Dialyzer Assessment (III of V) – (Safety Population Number and Volume of Saline Flushes)
- Appendix 16.2.5.8.4 Dialyzer Assessment (IV of V) – Clotting in Drip Chamber (Safety Population)
- Appendix 16.2.5.8.5 Dialyzer Assessment (V of V) – Clotting in Dialysis Filter (Safety Population)
- Appendix 16.2.5.9 Non-Study Procedures (Safety Population)
- Appendix 16.2.5.10 Prior and Concomitant Medications (Safety Population)

